1 PROTOCOL SYNOPSIS

Primary Objective: To evaluate the restoration and maintenance of thoracic kyphosis and coronal curve correction demonstrated through the surgical implantation of the K2M MESA Rail™ Deformity System as compared to literature reported outcomes for standard Cobalt Chrome (CoCr) rod systems in the treatment of Adolescent Idiopathic Scoliosis (AIS).

Study Design: Prospective, non-randomized (single-arm) multi-center study

Follow-Up Evaluations: Clinical evaluations of patients implanted with the MESA Rail Deformity System will be conducted at initial post-op, 3 months, 6 months, 12 months and 24 months post-procedure. Adverse events will be monitored continuously.

Effectiveness Assessments: Effectiveness measurements include the following:

- Quantitative and Qualitative Radiographic Assessments
 - Restoration and Maintenance of Thoracic Kyphosis
 - Coronal Curve Correction
 - Device Status
- Back and Leg Pain 10cm Visual Analog Scale (VAS)
- SRS-22r
- Perioperative Assessments
 - Estimated Blood Loss
 - Length of Operation
 - Time of Anesthesia
- Length of Hospital Stay
- Return to Work/School
- Use of Narcotics Post-Surgery
- Patient Satisfaction
- Odom's Criteria

Safety Assessments: Safety will be assessed by:

- The evaluation of all adverse events including but not limited to, device related, procedure related, and additional serious adverse events

Study Subjects: Patients eligible for study enrollment will present with AIS. Qualified AIS patients will have a confirmed Lenke 1 or Lenke 2 curve type. Subjects under evaluation will be ≥ 11 years old and ≤ 21 years old at time of surgery.

Device Evaluation Group: K2M, Inc. $\phi 5.5$ mm or $\phi 4.5$ mm MESA Rail Deformity System cleared for marketing and distribution under 510(k) K121630.

Comparative Device Group: Historical, literature control of reported results of $\phi 5.5$ mm or $\phi 4.5$ mm CoCr standard cylindrical rod systems (as applicable) in pedicle screw fixation for posterior stabilization.

Sample Size: Two-hundred four (204) total subjects with the MESA Rail Deformity System at up to 18 clinical sites, geographically distributed worldwide. Sites are considered a Principal Investigator and their Sub-Investigators who are covered by a singular

Institutional Review Board's (IRB's)/Ethics Committee's (EC's) oversight and approval.

Subject enrollment will be capped so that no single site contributes more than approximately 15% of the cases.

Investigator Selection:

- Appropriate patient population for trial indication
- An Investigator must have completed a minimum of three (3) surgeries using the MESA Rail Deformity System. If a surgeon does not have experience in using the MESA Rail system, their first three (3) patients will be considered roll-in patients and the results from these patients will be analyzed against the entire cohort to determine if a learning curve exists. If a surgeon has previously completed three (3) surgeries using the MESA Rail system, there will be no stratification of their data.
- Experience in clinical trial execution
- Dedicated research infrastructure
- Local institutional review board (IRB)/Ethics Committee (EC) for research oversight or ability to use central IRB/EC
- Standard of Care (SOC) compatible with or capable of complying with the protocol requirements including but not limited to:
 - Radiographic imaging per protocol (Section 5.3.3)
 - Use/Collection of patient reported outcome measures – Back and Leg VAS, SRS-22r
 - Follow-up evaluations at initial post-op, 3 months, 6 months, 12 months, and 24 months
- Insofar as possible, sites for the study will be distributed geographically and by type of institution and level of investigator experience, patient volume and research experience so that any unanticipated and potentially prognostic factors may then be balanced both geographically and demographically in the study arms.

2 INTRODUCTION

2.1 Study Purpose

The purpose of this study is to evaluate the restoration and maintenance of thoracic kyphosis and coronal curve correction using the K2M Ø5.5mm and Ø4.5mm (as appropriate) MESA Rail Deformity System compared to a standard Ø5.5mm or Ø4.5mm CoCr (as appropriate) rod system.

2.2 Background and Significance

Adolescent Idiopathic Scoliosis (AIS) is a complex three-dimensional structural deformity of the spine that occurs most commonly in girls between ages 10 and 18 with a prevalence rate of 2%–4%^{1,2}. Radiographically, it is diagnosed with a coronal plane angle of greater than 10 degrees, predominately right-sided curves. The prevalence of AIS with curves greater than 10 degrees is noted as 4:1 females to males.

The Lenke Classification Scheme comprehensively describes the thoracic as well as the thoracolumbar/lumbar curves seen in AIS, in a biplanar manner. In this evaluation, only patients who exhibit Lenke 1 or 2 curves will be enrolled in this study.

Curves that are less than 20 degrees at initial evaluation are generally observed for 4-6 months. For a 20 to 30 degree curve, bracing is generally started if there is >5 degree progression between visits. Operative intervention using standard cylindrical rods of Ø5.5mm or Ø4.5mm (patient and curve dependent) to correct the scoliotic curve is used when the curves are progressive and bracing is not effective and/or if the curve is generally greater than 45 degrees.

2.3 Device Description

The MESA Rail (K2M, Leesburg, VA) is a novel cross-sectioned rod providing increased stiffness characteristics while maintaining a diameter capable of use with MESA pedicle screws (unique one-step final locking, zero-torque technology® screws offered by K2M, Leesburg, VA) designed for use in adolescent patients. The K2M MESA Rail System was cleared for marketing and distribution under 510(k) K121630 in the US. It is approved for marketing in the UK, Australia, and New Zealand under UK- EU DOC-001; ARTG 154442, and 120213-WAND-8CQMDH.

2.4 Surgical Procedure

The implantation of the MESA Rail Deformity System should be performed according to the standard of care of the Investigator, and in accordance with the K2M's Instructions for Use and Surgical Technique Manual for the MESA Rail Deformity System.

2.5 Indications for Use

The MESA Rail is indicated for use with the MESA Spinal System, non-cervical, pedicle screw fixation devices for posterior stabilization as an adjunct to fusion for the following indications: trauma; spinal stenosis; curvatures (i.e., scoliosis, kyphosis; and/or lordosis); tumor; pseudoarthrosis; and failed previous fusion from T1-S1.

2.6 Benefits and Risks

2.6.1 Potential Benefits

There is no guarantee that the subject will experience any immediate or direct benefits with the use of this device system or for taking part in this study.

2.6.2 Potential Risks

Potential risks identified with the use of this device system include Proximal Junctional Kyphosis (PJK), flatback, or adjacent level breakdown, as well as those associated with any spinal surgery resulting in neurological, cardiovascular, respiratory, gastrointestinal compromise, or death.

A full listing of potential risks of the device and the surgical procedure can be found in Section **9.5 Potential Risks and Anticipated Adverse Events**.

2.7 Mitigation of Risks

Operative and acute periprocedural risks for the patients enrolled in this study are mitigated by restricting the use of the device to skilled neurological and orthopedic spine surgeons trained and experienced in the proper surgical technique to implant the respective devices. Long-term risks such as device disengagement/failure and pseudoarthrosis are mitigated by proper patient selection and implanting the devices in accordance with the Surgical Technique Manual for the MESA Rail Deformity System and use of the surgical instruments provided by K2M and by following accepted standard of care for this AIS population.

3 INVESTIGATOR/SITE SELECTION

The Investigators selected to participate in this clinical study will be responsible for conducting the study according to the requirements of the protocol. Each site will have a designated Principal Investigator and may have Sub-Investigators. Investigators/sites will be selected for participation in the study according to the following criteria:

The Investigator/Site must have:

- Expertise in clinical areas relevant to the study, including a background in spine surgery, sufficient experience in clinical research and an adequate patient population with adolescent spine disorders
- Completed a minimum of three (3) surgeries using the MESA Rail Deformity System. If a surgeon does not have experience in using the MESA Rail Deformity System, their first three (3) patients will be considered roll-in patients and the results from these patients will be analyzed against the entire cohort to determine if a learning curve exists. If a surgeon has previously completed three (3) surgeries using the MESA Rail system, there will be no stratification of their data.
- Experience in participating in clinical studies and have adequate personnel and a dedicated research infrastructure including a Study Coordinator to adequately perform the tasks required by the clinical protocol
- Local institutional review board (IRB)/Ethics Committee (EC) for research oversight or ability to use central IRB/EC
- A practice in a medical facility equipped appropriately to fulfill the surgical and patient contact requirements of the study
- A standard of care (SOC) compatible with or capable of complying with the protocol requirements including but not limited to:
 - Radiographic imaging per protocol (**Section 5.3.3**)
 - Use/Collection of patient reported outcome measures – Back and Leg VAS, SRS-22r
 - Follow-up evaluations at initial post-op, 3 months, 6 months, 12 months, and 24 months
- (Be willing to) sign a Clinical Research Agreement and abide by the agreement for the duration of the study.
- (Be willing to) provide financial disclosure; including updating the disclosure during the study if the financial status changes

The Investigators and practices in this trial are representative of the general user population of this type of device. Insofar as possible, sites for the study will be distributed geographically and by type of institution and level of investigator experience, patient volume and research experience so that any unanticipated and potentially prognostic factors may then be balanced both geographically and demographically in the study arms.

3.1 Investigator Training

Training sessions in proper surgical technique and trial performance for the Principal Investigator, all Sub-Investigators and research coordinators will be provided by the sponsor prior to initiation of the study at each investigational site.

4 STUDY METHODS

4.1 Study Design

Prospective, non-randomized (single-arm) multi-center study to evaluate the restoration and maintenance of thoracic kyphosis and coronal curve correction using the MESA Rail Deformity System compared to literature reported outcomes for standard Cobalt Chrome (CoCr) rod systems for the treatment of symptomatic AIS.

4.2 Treatment Group

Patients treated with the Ø5.5mm or Ø4.5mm MESA Rail Deformity System that had:

- Diagnosis of AIS requiring surgical treatment for selective thoracic/lumbar fusion with a minimum of five (5) instrumented vertebrae between T1-S1 as confirmed by patient history and radiographic studies. AIS cases must be classified as a Lenke type 1 or type 2 curve (lumbar modifiers and thoracic sagittal profiles will be noted but not restrictive). No cervical vertebrae are to be incorporated into the construct.
- An age at time of surgery of ≥ 11 years old and ≤ 21 years old.

4.3 Control Group

Literature reported outcomes of adolescent patients (≥ 11 years old and ≤ 21 years old) diagnosed with AIS for whom a Ø5.5mm or Ø4.5mm CoCr pedicle screw and rod system was used in surgical treatment.

4.4 Sample Size

Two-hundred four (204) total subjects with the MESA Rail Deformity System at up to 18 clinical sites, geographically distributed worldwide. Sites are considered a principal Investigator and their Sub-Investigators who are covered by a single Institutional Review Board's (IRB's)/Ethics Committee's (EC's) oversight and approval.

Subject enrollment will be capped so that no single site contributes more than approximately 15% of the cases.

5 STUDY OBJECTIVES/OUTCOMES

5.1 Primary Effectiveness Objective

The primary effectiveness objective is:

Restoration and maintenance of thoracic kyphosis and coronal curve correction.

- Quantitative assessment:
 - Cobb Angles – Coronal and Sagittal
 - Thoracic kyphosis as measured from the upper endplate of T4 to the lower endplate of T12
 - Lumbar lordosis as measured from the lower endplate of L1 to the upper endplate of S1

The increased stiffness of the MESA Rail is designed for the restoration and maintenance of thoracic kyphosis as well as coronal correction of deformities such as AIS after surgery. The restoration and subsequent maintenance of the thoracic kyphosis and coronal curve correction during surgery is expected to be as good as if not better than results reported for standard Ø5.5mm and Ø4.5mm CoCr pedicle screw and rod systems in these patient populations.

5.2 Primary Safety Objective

The primary safety objective is:

- The evaluation of all adverse events including device related, procedure related and additional serious adverse events

All adverse events will be documented on a continuous basis and reviewed by K2M Clinical Research Staff. Information regarding all device failures including instrument breakage, implant breakage, subsidence, migration, or expulsion will be captured.

5.2.1 Device and Procedure Related Adverse Events

Device and procedure related adverse events will be documented and reported to the sponsor, including the need for removals, revisions, re-operations or supplemental fixation required to modify the device.

5.3 Secondary Objectives

Secondary objectives are expected to further define the safety and patient outcomes for effectiveness of the K2M device. Secondary objectives include:

5.3.1 Visual Analog Scale

The severity of back and leg pain will be evaluated in all study subjects using a 10-cm visual analog scale (VAS). The study will employ a 15% improvement for success.

5.3.2 SRS-22r

Scoliosis and its treatment have a great impact on the quality of life of the affected patients. The Revised Scoliosis Research Society-22 (SRS-22r) is a specific questionnaire for spine conditions. It is applied to patients with idiopathic scoliosis, whose conditions and treatments have a great impact on their quality of life. The SRS-22r was created and revised with the purpose of evaluating this impact from the patient's point of view. The reviewed version contains 22 questions distributed into five domains: function/activity (FA), pain (P), self-image/appearance (SA), mental health (MH) and satisfaction with treatment (ST). The scores vary from 1 to 5, in which 5 is the best health quality of life of patients.

5.3.3 Radiographic Assessments

Quantitative and qualitative radiographic assessment of the pre-operative AP, lateral, and left and right lateral bending images, as well as post-operative AP and lateral images will be performed. **Please note:** All images must be from head to hip to ensure that all relevant landmarks and instrumentation are captured and all measurements can be completed.

Radiographic assessments being performed include:

- Quantitative assessment:
 - Identification of apex level
 - Pre-operative assessment of curve flexibility will be performed by comparing the Cobb angles on the left and right lateral bending radiographs with the pre-operative standing AP and Lateral radiographs and recording percentage change in the Cobb angle
 - Assessment of coronal and sagittal curve correction will be performed by comparing the Cobb angles on the pre-operative AP and lateral radiographs with the standing AP and Lateral radiographs at each post-operative visit and recording percentage change in the Cobb angle
 - Pre-operative Risser Score
 - Global sagittal balance as measured by the distance from the C7 plumb line to the perpendicular line drawn from the superior posterior endplate of the S1 vertebral body (Central Sacral Vertical Line (CSV))
 - If the C7 plumb line falls behind the CSV, global sagittal balance is negative
 - Pelvic incidence, as defined by pelvic tilt + sacral slope
- Qualitative assessment
 - Pre-operative Lenke type classification
 - Lumbar spine modifier (A, B, or C) and/ thoracic sagittal profiles (hypo, normal, hyper)
 - Device condition post-operatively

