12.2 Study Hypothesis

The primary objective of this study is to evaluate the effectiveness of the MESA Rail Deformity System in terms of restoring and maintaining thoracic kyphosis in the treatment of patients with symptomatic AIS. The primary effectiveness endpoint is the rate of overall subject success (minimal loss of thoracic kyphosis) at 24 months. The primary hypothesis of this trial is that the clinical performance of the K2M MESA Rail implant is non-inferior to the clinical performance achieved and achieved with fusion utilizing a standard Ø5.5mm or Ø4.5mm CoCr rod.

A PubMed literature review was conducted to assemble relevant publications utilizing results from posterior instrumentation fusion surgeries in patients with AIS. Searches included all peer-reviewed journals published between January 2000 and March 2013. Sample sizes, patient populations, evaluated variables, results, and recorded complications were assessed for each selected article. Only data regarding thoracic kyphosis measurements of single-stage posterior fusion cases were incorporated into the thoracic kyphosis table used for statistical analysis. Articles were entirely excluded from the statistical analysis if results combined data from multi-stage cases or if data were extracted through meta-analysis.

The following table gives the preoperative thoracic kyphosis measurements as well as the thoracic kyphosis measurements collected at the last follow-up period from all relevant posterior fusion surgeries in patients with AIS:

| Thoracic Kyphosis | | | | | | | | | |
|----------------------------------|-----|-------|------|---------|------|------|------|---------------------|-------------|
| paper # | n | Preop | | Last FU | | Diff | | Mean difference x N | Std Dev x N |
| | | Mean | SD | Mean | SD | Mean | SD | | |
| 1 ¹ | 9 | 31.9 | 10.4 | 26.0 | 9.8 | 5.9 | 10.1 | 53.1 | 90.9 |
| 1 | 3 | 31.0 | 9.5 | 29.7 | 5.5 | 1.3 | 7.5 | 3.9 | 22.5 |
| 1 | 34 | 28.2 | 13.0 | 26.5 | 11.0 | 1.7 | 12.0 | 57.8 | 408.0 |
| 1 | 9 | 23.0 | 8.0 | 23.0 | 11.0 | 0.0 | 9.5 | 0.0 | 85.5 |
| 1 | 60 | 26.7 | 13.0 | 25.0 | 9.6 | 1.7 | 11.3 | 102.0 | 678.0 |
| 1 | 31 | 22.8 | 11.0 | 25.7 | 8.8 | -2.9 | 9.9 | -89.9 | 306.9 |
| 2 ² | 83 | 23.0 | 12.0 | 20.2 | 8.4 | 2.8 | 11.4 | 234.9 | 946.2 |
| 3 ³ | 111 | 29.0 | 14.0 | 23.0 | 10.8 | 6.0 | 12.2 | 666.0 | 1354.2 |
| 3 | 299 | 22.0 | 14.1 | 22.0 | 10.3 | 1.0 | 5.0 | 299.0 | 1495.0 |
| Weighted Mean Difference and SD: | | | | | | | | 2.1 | 8.4 |

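### Section 5.3.3 records sagittal correction as percentage change in the Cobb angle, which is unstable when pre-operative thoracic kyphosis is near zero and reverses sign when it is negative

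*Combined protocol and SAP*

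**What the plan says.** Section 5.3.3 (Radiographic Assessments) gives one rule for both planes: "Assessment of coronal and sagittal curve correction will be performed by comparing the Cobb angles on the pre-operative AP and lateral radiographs" with the standing post-operative films "at each post-operative visit and recording percentage change in the Cobb angle". It does not say what to record when the sagittal baseline is zero, close to zero or negative. By the visit schedule (8.6.1), the rule applies at the initial, 6-, 12- and 24-month visits, which are the ones with X-rays.

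Section 4.2 has the thoracic sagittal profile noted but does not restrict entry on it, and 5.3.3 lists hypokyphosis among the profiles to be recorded.

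The primary comparison uses another scale. Sections 12.2, 12.3 and 12.5 state the hypothesis, the sample size and the test in degrees, against a reference of 2.2. Section 5.1 has T4-T12 kyphosis measured as an angle.

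The only baseline information is the literature table in 12.2. Its largest row (n, pre-operative mean and SD, follow-up mean and SD) reads "299 | 22.0 | 14.1 | 22.0 | 10.3".

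**The concern.** Percentage change works for a coronal curve that is large before surgery. Section 2.2 puts the usual operative threshold at about 45 degrees. Thoracic kyphosis is different, because in the 12.2 table its SD is large relative to its mean, and a thoracic spine can be flat or lordotic. The same 4-degree increase in kyphosis then gives very different percentages:

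- from 30 degrees: 4/30 = +13%
- from 22 degrees: 4/22 = +18%
- from 5 degrees: 4/5 = +80%
- from 2 degrees: 4/2 = +200%
- from -2 degrees: 4/(-2) = -200%

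Restoring kyphosis is part of the primary effectiveness objective, and this is the plan's only instruction on how sagittal correction is recorded visit by visit. If the percentages were averaged, a handful of subjects could set the result, and its sign could disagree with the change in degrees.

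**Working it through.** **1. The plan's own figure.** Section 12.3 uses a mean of 4.0, a reference of 2.2 (difference 1.8), SD 8.4, two-sided 0.05 and 80% power. The normal formula gives (8.4 × (1.960 + 0.842) / 1.8)² = 170.9. The exact one-sample t-test has power 0.798 at 172 and 0.8003 at 173. Then 173 / 0.85 = 203.5, rounded up to 204. Both stated numbers reproduce, and both rest on degrees.

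**2. Share of small or negative baselines.** Inputs are the pre-operative mean and SD of each row of the 12.2 table. Assuming normality and angles recorded with their sign, the share below c is Φ((c - mean)/SD). For the n=299 row, Φ(-22.0/14.1) = 5.9% and Φ((5 - 22.0)/14.1) = 11.4%.

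| n | Mean | SD | Below 0 | Below 5 |
|---|---|---|---|---|
| 9 | 31.9 | 10.4 | 0.1% | 0.5% |
| 3 | 31.0 | 9.5 | 0.1% | 0.3% |
| 34 | 28.2 | 13.0 | 1.5% | 3.7% |
| 9 | 23.0 | 8.0 | 0.2% | 1.2% |
| 60 | 26.7 | 13.0 | 2.0% | 4.8% |
| 31 | 22.8 | 11.0 | 1.9% | 5.3% |
| 83 | 23.0 | 12.0 | 2.8% | 6.7% |
| 111 | 29.0 | 14.0 | 1.9% | 4.3% |
| 299 | 22.0 | 14.1 | 5.9% | 11.4% |

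Weighted by n (total 639):
- below 0: 24.5/639 = 3.8%, and 0.038 × 204 ≈ 8 subjects
- below 5: 50.3/639 = 7.9%, and 0.079 × 204 ≈ 16 subjects

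As the other extreme, a strictly positive gamma with the same means and SDs (shape (mean/SD)², scale SD²/mean) gives none below 0 and 2.8% below 5, about 6 of 204.

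**3. Effect on a mean percentage.** The model is the n=299 row: bivariate normal, SDs 14.1 and 10.3, both means 22.0 (no true change), 173 subjects per trial. The correlation r is set so that the SD of change matches a figure in the plan, with r = (14.1² + 10.3² - SD²) / (2 × 14.1 × 10.3) = (304.9 - SD²) / 290.5.

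- SD 5.0, printed in that row: r = 279.9/290.5 = 0.96
- SD 8.4, the planning value: r = 234.3/290.5 = 0.81

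| SD of change | 95% range, mean percentage change | 95% range, mean change in degrees (1.96 × SD/√173) |
|---|---|---|
| 5.0 | about -230% to +215% | ±0.75 |
| 8.4 | about -340% to +360% | ±1.25 |

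The percentage limits are approximate. Another set of 20,000 trials gave -220% to +235% and -313% to +328%. This is expected: a ratio whose denominator has positive density at zero has no finite mean, so the average does not settle as n grows. With a true 4-degree mean change, the mean percentage had the opposite sign to the change in about 26-28% of simulated trials.

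**4. Dependence on the normal assumption.** With a strictly positive gamma baseline (22.0, SD 14.1) and change independent of baseline, the mean percentage stays within about -16% to +16%. The extreme ranges in step 3 therefore need baselines that reach zero.

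**The case against.** The strongest reply is that little depends on this instruction. The angles are measured by a central laboratory (12.8), so change in degrees can be derived at every imaging visit. Section 12 names no analysis of the percentage. Section 12.7 allows a median where appropriate, and the median is far better behaved: about -11% to +2% across simulated trials with SD 8.4 and no true change. A secondary measure on a different scale from the primary is not in itself an error. All of this stands, and it keeps the point small. It does not rescue the rule, which still prescribes a wrong-signed or exploding value for some subjects.

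Stronger readings are tempting but not supported:

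- A reader might infer from the table that many subjects are affected. It gives no individual values, ranges or counts near zero. The 5.9% and 11.4% belong to one row, which has the lowest mean and the largest SD of the nine. Each of the others is at 2.8% or less below zero.
- A reader might simulate with a middling correlation such as 0.5 and get wider ranges. That implies a change SD of √(304.9 - 0.5 × 290.5) ≈ 12.6 degrees, against the 5.0 printed in the same row and the 8.4 used for planning.
- A reader might extend the point to lumbar lordosis. The documents give no lordosis baseline and nothing that puts it near zero.

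**Conclusion.** The point holds as a minor defect in a secondary recording instruction. For the sagittal plane, percentage change is ill-behaved near zero and reverses sign below it, such patients may enrol, and the plan has no rule for them. The share is small and assumption-dependent: about 0-4% of subjects at or below 0 degrees and about 3-8% below 5, the lower ends from a strictly positive gamma and the upper ends from a normal distribution.

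If baselines are roughly normal, that share is enough to make a mean percentage uninformative. If they are strictly positive, the instability is much milder. A reader might infer that the primary result is at risk. It is not, because the hypothesis, the test and the sample size of 173 (204 enrolled) are all in degrees.

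**What to change.** In 5.3.3, separate the two planes. For example: at each post-operative visit with radiographs, correction of T4-T12 thoracic kyphosis is recorded and summarised as change in degrees from the pre-operative film, signed as in the primary comparison; coronal correction is recorded as percentage change in the Cobb angle.

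The cost is one sentence. It needs no new measurement or visit, leaves the sample size unchanged, and puts the visit-level kyphosis data on the scale of the primary test.
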